7.1.4. Health-Related Quality of Life Assessments

The SF-36 v2 and EQ-5D-5L will be completed by study patients at visits specified in the [Time and Events Table](#) to measure changes from baseline in health-related quality of life. Proven translations will be used for non-English speaking patients whenever possible. An administrator will facilitate completion of the questionnaires by the patients, but will not complete the forms for the patients. The administrator will establish a rapport with the patient, emphasize the importance of completing the form, and serve to answer questions and address concerns. The questionnaires should be completed by patients before seeing the Investigator at the visit.

7.2. Safety Assessments

7.2.1. Physical Examinations, Vital Signs and 12-lead ECGs

A complete physical examination (including evaluation of general appearance/mental status, head, eyes, ears, nose, throat, and the following body systems: dermatologic, cardiovascular, respiratory, gastrointestinal, musculoskeletal and neurologic) will be performed at visits indicated in the [Time and Events Table](#). Findings must be recorded in the source documents.

Any new or worsening findings upon physical examination need to be recorded as adverse events.

Body weight will be measured as part of the physical examinations. Height needs to be recorded at screening only, except for adolescents (12 to 17 years old) in whom height will also be included as part of all physical examinations. BMI will be calculated in the EDC from the body weight and height measurements.

Vital signs will be measured during screening and on each scheduled study day as indicated in the [Time and Events Table](#). Sitting blood pressure, pulse rate, and body temperature will be measured. All vital signs assessments will be performed after the patient has rested for at least three minutes.

12-lead ECGs will be performed at visits indicated in the [Time and Events Table](#). Findings must be recorded in the source documents. The ECG will be performed after the patient has rested for three minutes in a supine position. Abnormal and clinically significant changes in ECG per Investigator's assessment compared to baseline screening need to be recorded as adverse events.

7.2.2. Clinical Safety Laboratory Assessments

The following tests will be performed via Central Laboratory at the visits identified in the [Time and Events Table](#).

- Hematology: hemoglobin, hematocrit, RBC count, WBC count with differential, platelet count, mean cell hemoglobin, mean cell hemoglobin concentration, mean corpuscular volume;

- Serum Chemistry: liver panel (total and fractionated bilirubin, lactate dehydrogenase, aspartate aminotransferase, alanine aminotransferase), renal panel (blood urea nitrogen, creatinine), creatine phosphokinase (CPK), albumin, sodium, potassium, magnesium, bicarbonate, chloride, calcium, inorganic phosphorus, glucose, total protein, alkaline phosphatase, total cholesterol, uric acid, serum amylase, and serum lipase;
- Coagulation: PT and INR if retest is performed because of ALT and/or AST >3x ULN;
- Urinalysis: at the central laboratory, nitrite, blood, and protein, will be tested. If positive, microscopy will be performed;
- Virology (measured only at screening and may be measured at the local laboratory): hepatitis B surface antigen, hepatitis C antibodies, HIV 1 and 2 antibodies; virology tests done within 6 weeks prior to screening are acceptable for eligibility assessment. Results from prior tests performed at the local laboratory must be recorded in the EDC system;
- TB screen: only one of the following is needed: interferon γ release assay (IGRA), tuberculin purified protein derivative (PPD) skin test, or chest radiograms (X rays or CT scan); chest radiography done within 6 weeks prior to screening is allowed for eligibility assessment.

7.2.3. Complement Panel

The following panel will be measured in all patients based on recommendations from a consensus panel ([Pickering et al., 2013](#)):

- Plasma C3a, C5a, C5b-9, and C5;
- Serum C3 and C4;
- Serum C3 nephritic factor;
- Plasma complement factor H and factor B;
- Serum factor H auto-antibody;
- Serum paraprotein detection;
- CFHR5 mutation

Results from tests performed within 4 weeks prior to screening will be allowed for the study. For CFHR5 mutation, results from tests performed any time in the past will be allowed. If these tests have not been performed previously in a patient, samples need to be collected prior to Day 1 for measurement either at the local laboratory (if capabilities exist) or at the central laboratory. Results from these tests do not need to be available prior to start of dosing on Day 1, except for C5b-9 which is needed for eligibility assessment. Results from tests performed at the local laboratories need to be recorded in the EDC.

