Avacopan/Placebo dispensing		X ^c			X	X	X	X	X													
Avacopan dispensing										X		X		X		X						
Avacopan/Placebo double-blind dosing		X→	→	→	→	→	→	→	→		→X											
Avacopan dosing											X ^h	→	→	→	→	→	→	→	X ⁱ			
Avacopan/Placebo accountability					X	X	X	X	X		X		X		X		X		X			X
PD plasma/serum sample collection ^j		X ^c	X	X	X		X		X		X	X	X		X				X	X	X	X
Blood sample for lymphocyte subset analysis ^k		X ^c	X	X	X		X				X				X				X			X
PD urine sample collection		X ^c	X	X	X		X		X		X	X	X		X				X			X
PK plasma sample collection		X ^c	X	X	X		X		X		X	X	X		X				X	X	X	X
Concomitant medications	X	X	X	X	X	X	X	X	X	X	X	X	X	X	X	X	X	X	X	X	X	X
Adverse event assessment		X	X	X	X	X	X	X	X	X	X	X	X	X	X	X	X	X	X	X	X	X

^a Week 1 through 20 visits may occur within a ± 2 day window. Week 26 through 60 visits may occur within a ± 7 day window.

^b Physical examination will include body weight measurements. Height will be measured only at Screening in adults, but at all visits for adolescents.

^c These procedures must be performed before taking the first dose of avacopan.

- ^d Any one of the following may be done for TB screening: Interferon γ release assay (IGRA), tuberculin purified protein derivative (PPD) skin test, or chest radiography (done within 6 weeks prior to Screening or done during Screening).
- ^e Renal biopsy required for eligibility if not performed within 12 weeks prior to screening; renal biopsy -2 weeks prior to the Week 26 visit, and should be completed before open-label medication is started.
- ^f In adolescents, only the baseline and one follow-up renal biopsy (at Week 26) are required; the 52-week biopsy is optional.
- ^g Plasma C3a, C5, C5a, and C5b-9; serum C3, C4, and C3 nephritic factor; plasma complement Factor H and factor B; serum factor H auto-antibody; serum paraprotein detection; CFHR5 mutation. Results obtained within 4 weeks prior to screening or any time in the past for CFHR5 mutation will be acceptable for the study.

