4.3. Exclusion Criteria

1. Pregnant or nursing;
2. Tubulointerstitial fibrosis appears to be more than 50% based on standard assessment using trichrome staining of the renal biopsy;
3. Use of eculizumab or another anti-C5 antibody within 26 weeks prior to dosing;
4. Secondary C3 disease, e.g., infection-associated disease, or associated with another systemic or autoimmune disease; presence of a monoclonal spike on serum or urine protein electrophoresis or immunofixation assay;
5. Currently on dialysis or likely will require dialysis within 7 days after screening;
6. History or presence of any form of cancer within the 5 years prior to screening, with the exception of excised basal cell or squamous cell carcinoma of the skin, or carcinoma in situ such as cervical or breast carcinoma in situ that has been excised or resected completely and is without evidence of local recurrence or metastasis;
7. Positive hepatitis B virus (HBV), hepatitis C virus (HCV), or human immunodeficiency virus (HIV) viral screening test indicative of acute or chronic infection;
8. Evidence of tuberculosis based on interferon γ release assay (IGRA), tuberculin purified protein derivative (PPD) skin test, or chest radiography done at screening or within 6 weeks prior to screening; a CT scan or chest X-ray are not mandatory if evidence of tuberculosis was excluded by any of the other methods specified above;
9. Active uncontrolled infection;

10. WBC count less than 3500/ μ L, or neutrophil count less than 1500/ μ L, or lymphocyte count less than 500/ μ L before start of dosing;
11. Evidence of hepatic disease; AST, ALT, alkaline phosphatase, or bilirubin >3x the upper limit of normal before start of dosing;
12. Currently using a strong inducer of the CYP3A4 enzyme, such as carbamazepine, phenobarbital, phenytoin, rifampin, or St. John's wort;
13. Known hypersensitivity to avacopan or inactive ingredients of the avacopan capsules (including [REDACTED]) or inability to swallow the capsules;
14. Participated in any clinical study of an investigational product within 30 days prior to screening or within 5 half-lives after taking the last dose; and
15. History or presence of any medical condition (for example: contraindication to local anesthesia required for renal biopsy, or recurring serious infections) or disease which, in the opinion of the Investigator, may place the patient at unacceptable risk for study participation.

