6. STUDY PROCEDURES

6.1. Screening and Enrollment

Informed Consent (and Assent, if relevant) must be obtained prior to performance of any study-specific tests or evaluations. Within a period not to exceed 42 days prior to randomization, patients will undergo the following evaluations to determine their eligibility for study participation:

- Recording of demographic data and relevant medical history in the EDC;
- Recording of all prior medications for C3G for the 12-month period prior to screening in the EDC;
- Recording of all other prior medications for the 6-month period prior to screening in the EDC;

- Recording of all other concomitant medications on the screening day(s) in the EDC, including alcohol intake, recreational drug use, non-prescription medications, herbal preparations or special diets;
- A physical examination will be performed; body weight and height will be measured;
- Vital signs (temperature, sitting blood pressure, heart rate) will be measured after at least 3 minutes of rest;
- A 12-lead ECG will be performed after at least 3 minutes of rest in a supine position;
- Serum pregnancy test (in women of childbearing potential);
- Virology assessments as detailed in [Section 7.2.2](#), unless done within 6 weeks prior to screening;
- At least one of the following tests to exclude tuberculosis: interferon γ release assay (IGRA), tuberculin purified protein derivative (PPD) skin test, or chest radiography (X rays or CT scan); tests performed within 6 weeks prior to screening are allowed to assess eligibility;
- Serum chemistry and hematology tests (results from tests done within 72 hours prior to screening may be used for eligibility assessment);
- A clean catch, midstream urine sample will be collected for urinalysis, and urine protein, urine albumin and urine creatinine measurement for UPCR and UACR;
- A renal biopsy will be taken if renal histology has not been performed within 12 weeks prior to screening;
- Complement profiling as detailed in [Section 7.2.3](#). Results obtained within 4 weeks prior to screening, or any time in the past for CFHR5 mutation, will be acceptable for the study. Also, the results from these tests do not need to be available before start of dosing on Day 1, except for the C5b-9 levels that are needed for eligibility assessment.

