Results from tests performed within 4 weeks prior to screening will be allowed for the study. For CFHR5 mutation, results from tests performed any time in the past will be allowed. If these tests have not been performed previously in a subject, samples need to be collected prior to Day 1 for measurement either at the local laboratory (if capabilities exist) or at the central laboratory. Results from these tests do not need to be available prior to start of dosing on Day 1, except for C5b-9 which is needed for eligibility assessment. Results from tests performed at the local laboratories need to be recorded in the EDC.

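### The serum paraprotein result that exclusion 4 depends on is not required before Day 1, so a patient with no earlier result could be randomised and dosed before that exclusion is checked

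*Protocol*

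**What the plan says.** Exclusion 4 (Protocol Section 4.3, repeated in the Synopsis) covers secondary C3 disease and adds "presence of a monoclonal spike on serum or urine protein electrophoresis or immunofixation assay".

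The complement panel in Protocol Section 7.2.3 includes "Serum paraprotein detection". Sections 7.2.3 and 6.1 accept panel results from the 4 weeks before screening. Where the tests have not been done before, Section 7.2.3 says that "samples need to be collected prior to Day 1 for measurement either at the local laboratory (if capabilities exist) or at the central laboratory". That sets a deadline for the sample, not for the result.

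On the result, three places agree:

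- Protocol Section 6.1: "the results from these tests do not need to be available before start of dosing on Day 1, except for the C5b-9 levels"
- Protocol Section 7.2.3: "Results from these tests do not need to be available prior to start of dosing on Day 1, except for C5b-9 which is needed for" (the purpose given is the assessment of eligibility).
- SAP 2.3.7.3 (Complement Panel): "Results from these tests do not need to be available prior to start of dosing on Day 1, except for C5b-9"

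Other Protocol text points the other way. Section 6.1 closes by assuming that screening is complete and every criterion is satisfied before the patient goes forward. Sections 3.4 and 6.2 start treatment only in eligible patients. Section 8.10 rules out waivers.

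**The concern.** An exclusion criterion protects the trial only if its result is known before the patient is committed. Here the laboratory result that bears on exclusion 4 is placed among those that may arrive after the first dose. A site can follow the specific timing rule correctly and still dose a patient whom the criterion bars.

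Two things are at stake. The patient would take study drug in a trial that the protocol meant to keep closed to them. The primary comparison would also include someone whose disease is regarded as secondary, in a primary population of only about 44. The deviation would come from the protocol's own schedule rather than from a site error.

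**Working it through.** The plan states no figure here to reproduce. The check sets the passages side by side.

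1. **Which scheduled test can show a spike?** The Time and Events Table has no row for electrophoresis or immunofixation. Paraprotein appears only in the footnote to complement profiling: "serum factor H auto-antibody; serum paraprotein detection; CFHR5 mutation". The screening list in Section 6.1 and the laboratory list in Section 7.2.2 add no other such test. Serum paraprotein detection in the panel is therefore the only scheduled one.

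2. **When must its result be known?** Sections 6.1 and 7.2.3 and SAP 2.3.7.3 release every panel result except C5b-9 from being available before dosing. Paraprotein is not in the exception.

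3. **When is the patient committed?** Section 6.2 places stratification and randomisation on Day 1, before the first dose.

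4. **Which patients are exposed?** There are three cases:
   - An earlier result is in hand, from routine care (Section 6.1) or from the 4 weeks before screening (Section 7.2.3). Exclusion 4 can be checked.
   - There is no earlier result, but the screening sample is reported before Day 1. Exclusion 4 can be checked.
   - There is no earlier result and the sample is still pending on Day 1. The timing rule permits dosing, and the scheduled test cannot yet inform exclusion 4.

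   The gap is confined to the third case.

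5. **What happens in the analysis?** SAP 3.2.2 defines intent-to-treat as randomised and dosed. It leaves out only patients with a baseline activity score of 0 and ongoing patients who have not completed Week 26. Late-found ineligibility is not a reason for removal. SAP 3.2.4 lists significant eligibility deviations among the matters to consider for per-protocol exclusion. Protocol Section 8.10 provides sensitivity analyses without patients who have significant deviations, and SAP 4.2 assesses such deviations through the per-protocol analyses. The primary analysis therefore keeps the patient.

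6. **Weight of one patient.** With about 44 patients in a stratum and 22 per arm (Protocol Section 3.1): 1/44 = 0.0227, or 2.3% of the stratum; 1/22 = 0.0455, or 4.5% of an arm.

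**The case against.** The best reply is that the timing sentence permits dosing without the result but does not require it, and does not repeal exclusion 4. Sections 3.4, 6.1 and 6.2 all make eligibility a condition of Day 1, waivers are barred, and many patients may already have had electrophoresis in routine care. A careful site would wait. This stands as a limit on the point. A reader might infer that exclusion 4 cannot be enforced at all, and the documents do not support that. It does not remove the conflict, however. Earlier results are allowed but not required, and a general eligibility statement does not cancel a specific sentence telling sites that the result may come later.

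A reader might also think the C5b-9 exception misplaced, because no listed criterion names C5b-9. That goes too far. Section 3.1 lets the lower stratum close early, after which C5b-9 would decide whether a patient can enter. The exception is reasonable; it is only incomplete.

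Exclusion 4 also mentions urine, and no urine paraprotein test is scheduled. A reader might count this as a second gap. A known urine spike still excludes, the wording does not demand both tests, and other exclusions, such as cancer history, also have no scheduled test behind them. No urine test is asked for here.

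Finally, keeping an ineligible patient in an intent-to-treat analysis is ordinary practice, and because the panel is measured in all patients, such a patient can be identified. Both points are fair. They make the analysis consequence manageable, but they do not address entry into the trial.

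**Conclusion.** The inconsistency is real and appears in three places. Exclusion 4 depends on a finding whose only scheduled test is released from being reported before dosing. A patient with no earlier result and a pending sample could be randomised and dosed before the criterion is checked, and would then remain in the primary analysis population.

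The size cannot be stated as a count. The documents give no prevalence of monoclonal spike, no share of patients with earlier results and no laboratory turnaround time. Any expected number would rest on assumed values for all three. What can be said is that each such patient would be about 2.3% of a 44-patient stratum. A reader might infer that patients with paraprotein-associated disease have in fact been enrolled; the documents show only that this could happen. Nor does the rule in Section 4.1 against replacing patients add to the problem, since it concerns early drop-outs, and a patient found ineligible need not drop out.

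The conclusion rests on reading the three timing statements as they stand, with paraprotein among the panel tests they refer to.

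**What to change.** Reconcile Protocol Sections 6.1 and 7.2.3 and SAP 2.3.7.3 with exclusion 4 and with the eligibility statement that closes Section 6.1. The simplest way is to add serum paraprotein detection to the existing C5b-9 exception in all three places, so that a result is in hand before randomisation. The result may come from the screening sample or from an earlier test that the protocol already accepts.

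The cost is one sentence in three places and an occasional wait for a result. The serum sample is already part of screening, which lasts up to 42 days. The wait is avoided only if the sample is drawn early enough, because the present text asks only that it be taken before Day 1.

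SAP 8.1 still refers to patients who may be enrolled later, so the change can have effect. For patients already dosed, paraprotein results that arrived after Day 1 should be checked in the blinded data review that SAP 8.1 places before the data freeze. Any eligibility deviation found should be recorded there, with the per-protocol decision made before unblinding.

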7.2.4. Adverse Events

An adverse event (AE) is defined as any untoward medical occurrence associated with the use of a drug in humans, whether or not considered drug related. An adverse event could therefore be any unfavorable and/or unintended sign (including abnormal laboratory findings), symptom, or disease temporally associated with the use of the drug, whether or not considered related to the drug. This definition includes intercurrent illnesses or injuries, and exacerbation of pre-existing conditions.

An unexpected adverse event is an adverse event that is not identified in nature, severity, or frequency in the current Investigator's Brochure, or that is of greater severity than expected based on the information in the Reference Safety Information listing within the Investigator's Brochure.

All adverse events occurring in patients who have been randomized to treatment will be recorded in the EDC system and will be reported in accordance with regulatory requirements. Adverse events reported prior to commencement of administration of blinded study medication will be considered pre-treatment events and will also be captured.

All adverse events will be monitored until resolution or, if the adverse event is determined to be chronic, until a cause is identified. If an adverse event remains unresolved at the conclusion of the study, a clinical assessment will be made by the Investigator and the Sponsor's Medical Monitor to determine whether continued follow-up of the adverse event is warranted.

7.2.4.1. Adverse Event Severity Assessment

The severity of each adverse event will be determined by the Investigator using the following scale:

- Mild (Grade 1): no limitation of usual activities
- Moderate (Grade 2): some limitation of usual activities
- Severe (Grade 3): inability to carry out usual activities
- Life-threatening (Grade 4): an immediate risk of death
- Death (Grade 5)

It is not necessary to utilize Common Terminology Criteria for Adverse Events (CTCAE) grading for clinical events. However, in terms of lab values, the lab CTCAE criteria may be used for severity assessment. If there is a clinical AE that is related to a lab abnormality, the AE should be reported as the clinical event, where possible.

7.2.4.2. Causality Assessment

The relationship of avacopan/placebo to an adverse event will be determined by the Investigator and Sponsor based on the following definitions:

- Probably Not Related: the adverse event was more likely explained by causes other than avacopan/placebo.
- Possibly Related: there is evidence for a reasonable possibility that avacopan/placebo administration caused the adverse event.

7.2.4.3. Serious Adverse Events

A serious adverse event (SAE) is defined as any untoward medical occurrence that at any dose:

- Results in death;
- Is life-threatening (i.e., the patient was, in the opinion of the Investigator, at immediate risk of death from the event as it occurred);
- Requires or prolongs hospitalization;

- Results in persistent or significant disability or incapacity;
- Is a congenital anomaly or birth defect;
- Is an important and significant medical event that, based on appropriate medical judgment, may jeopardize the patient and/or may require medical or surgical intervention to prevent one of the other outcomes defining serious.

Elective surgery already known during screening to occur in the course of the study, and elective hospitalizations for convenience of the patient which are clearly unrelated to any medical condition and agreed upon between the Investigator and the patient prior to randomization, will not have to be reported as SAEs.

